Main study participants will be tested using real-time PCR testing of swabs, and these data will be used to identify SARS-CoV-2 infection events for primary analysis. Some main study participants may also receive SARS-CoV-2 testing through university testing systems, or through outside providers, and will be asked to report any positive test results to the study team. Any positive SARS-CoV-2 test results for main study participants – based on PCR testing of study swabs or based on other testing systems indicative of acute infection – will trigger

swabbing of contacts in the PCC and enrollment and swabbing of contacts in the CACC. Secondary analyses of vaccine efficacy will include SARS-CoV-2 infection events diagnosed through any testing system – either by PCR testing of study swabs or through outside testing.

The two contact cohorts – the PCC and the CACC – will both be used for analyses of the vaccine effect on secondary transmission, as described below.

The study is “time-driven”, ie, the primary analysis will occur when all participants have completed the 4 months follow-up. The number of primary endpoint infection events that accrue in the study is random and will depend on the level of SARS-CoV-2 incidence in each arm.

Table 6-1 Study Analysis Sets and Definitions

Analysis Set	Definition	Analyses
Full Analysis Set (FAS)	Main Study participants who enroll in the study	Primary efficacy analyses*
Day 29 Negative (D29-) Set	Participants in the FAS without PCR-confirmed infection on or before Day 29 ⁹	Primary efficacy analyses*
Per-Protocol (PP) Set	Participants in the D29- set who received all planned immunizations at the designated immunization visits within specific visit windows	Secondary efficacy analyses*
Day 29 Negative Transmission Set (D29-TS)	Participants in the D29- set and their contacts in the Prospective and Case Ascertained Contact Cohorts	Primary analyses of secondary transmission*
Case-Cohort Immunogenicity Set (ccIS)	Subset of the FAS that is randomly sampled for measurement of immunological markers and fully described in study SAP	Immunology marker analyses

*These analysis sets include participants without regard to baseline SARS-CoV-2 status. However, primary

efficacy analyses will condition on baseline SARS-CoV-2 seronegative status.

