6.4.3 Vaccine efficacy (VE) analyses against SARS-CoV-2 infection

The time origin for all analyses of SARS-CoV-2 infection is enrollment. We define the time of diagnosis of the SARS-CoV-2 infection endpoint as the collection time of the first daily swab with a positive PCR test. The time of diagnosis of lab-confirmed clinical COVID-19 disease is the first time of reported qualifying COVID-19 symptoms that occurs simultaneously or after the diagnosis of the SARS-CoV-2 infection endpoint. The time of diagnosis of asymptomatic SARS-CoV-2 infection is the collection time of the first sample with a positive PCR test result or seroconversion without any prior or subsequent reporting of symptoms that led to confirmation of a COVID-19 disease endpoint. The time of diagnosis of SARS-CoV-2 seroconversion is the collection time of the first sample seropositive for SARS-CoV-2, for participants SARS-CoV-2 seronegative at baseline; the SAP will specify criteria for defining seroconversion (re-infection)

for individuals SARS-CoV-2 seropositive at baseline. The failure times of participants never observed to be diagnosed with a given clinical endpoint will be right-censored at the date of last contact at which endpoint status was assessed or study termination. The failure times of participants reporting receipt of COVID-19 vaccination outside the study will be right-censored at the date of first outside vaccination.

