6.4.3.2 Secondary VE Analyses

The primary analysis of VE against SARS-CoV-2 infection will be repeated in the FAS and D29- sets but including baseline seropositive participants [Secondary Objective 5]; and in the PP set [Secondary Objective 9]. The same methods also apply to evaluating VE against seroconversion [Secondary Objective 2] and VE against COVID-19 disease [Secondary Objective 3]. Additional secondary VE analyses will be conducted where the time of SARS-CoV-2 infection diagnosis is defined as the earliest of the first positive SARS-CoV-2 test result based on either PCR testing of nasal swabs or external SARS-CoV-2 testing.

While the primary analysis of VE against SARS-CoV-2 infection will censor the follow-up time of participants who receive outside COVID-19 vaccination at the time of first outside vaccination, a secondary analysis will be performed that includes infection events and person-time that accrue following outside vaccination with the Moderna COVID-19 Vaccine. Participants receiving outside vaccination other than Moderna COVID-19 Vaccine will continue to be censored at the time of outside vaccination. A time-varying Cox model will be used for inference, per methods in the study SAP.

The asymptomatic SARS-CoV-2 infection endpoint [Secondary Endpoint 8] is defined by the PCR tests of daily swabs and serologic diagnostic testing schedule at month 0, 2, and 4. The occurrence of a COVID-19 disease event is a competing risk because the occurrence of COVID-19 disease precludes the possibility of occurrence of a subsequent asymptomatic SARS-CoV-2 infection event. Therefore, VE against asymptomatic SARS-CoV-2 infection will be assessed using methods accounting for COVID-19 disease as a competing risk. The SAP will provide details.

Vaccine efficacy against the infection and disease endpoints as measured by the reduction in the cumulative incidence of the endpoint by Month 4, will also be evaluated using the Nelson-Aalen estimator of cumulative incidence. This analysis does not rely on the proportional hazards assumption and has a simple interpretation that lends itself to understanding of population effects.

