3.2 Statistical Analysis Issues

3.2.1 Time scales

The analysis will utilize two different time scales. “Calendar time” will be defined as time since enrollment of the first study participant. “Study time” will be defined as time from either the first

nasal swab (if the first swab result was negative) or 90 days after the first swab (if first swab positive). Note that while randomization would be the ideal origin for study time, some participants did not begin swabbing until days or even weeks into the study, and infection status and timing of infection cannot be determined prior to the initiation of swabbing.

3.2.2 *Incident infection*

An incident SARS-CoV-2 infection will be defined as the first instance of a positive PCR result that follows at least one negative PCR result. Therefore, for participants who are baseline SARS-CoV-2 positive (i.e. seropositive at first blood collection or PCR positive on first swab), an incident infection occurs only 90 days after the first swab and once there is at least one negative PCR followed by a positive PCR.

3.2.3 *Seroconversion*

A seroconversion event will be defined as the first instance of a positive serology result that follows at least one negative serology result.

3.2.4 *Censoring approaches*

The following analyses will use the following censoring approaches (as specified in analytical approach). For the primary endpoint, “test” refers to a PCR test of a nasal swab. For the secondary endpoint of seroconversion, “test” refers to serology of a blood sample.

- ITT censoring: In the SoC arm, follow-up time is censored at the last negative test prior to end of study vaccination or the last negative test if the participant is not vaccinated on study (both are ignored if the first positive test occurs after the last negative test). In the Immediate Vaccination arm and the Vaccine Declined group, follow-up will be censored at the last negative test (ignored if the first positive test occurs after the last negative test). The timing of any test is considered to be the day on which the assay was collected, where day is defined from 3AM to 3AM of local time of the site.

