3.2.6 SARS-CoV-2 exposure

Given the open-label nature of the study, it is possible that individuals in the Immediate Vaccination, SoC, and Vaccine Declined groups have different exposure to SARS-CoV-2. While the randomized groups are ensured to balance with respect to baseline factors, individuals in the Vaccine Declined Group are likely to differ from those in the randomized groups based on both baseline and time-varying factors related to exposure. Imbalanced exposure between groups may lead to bias in analyses that compare endpoint distributions between groups. A series of analyses will explore predictors of SARS-CoV-2 exposure based on baseline SARS-CoV-2 negative participants in the SoC group. Separate but identical analyses will explore predictors of exposure in the Vaccine Declined group.

The outcome of interest will be time to incident infection. Calendar time will be the time scale and participants will be censored using 'outside testing censoring'. Baseline and time-varying variables listed above in Section 3.2.5 will be screened univariately for their associations with SARS-CoV-2 infection based on Cox proportional hazards models that stratify on study site. Variables with p-values less than 0.10 will be retained. Retained baseline variables will be screened further to remove highly correlated variables; for pairs with absolute value of Spearman correlation > 0.90 , a randomly chosen member of the pair will be retained. Cox regression with lasso penalty, stratified on study site and implemented with glmnet and with the retained variables from the previous step, will be used to derive a 'risk score' that is used for

adjustment in multiple analyses described below. The linear predictor of the penalized Cox model will be used as the risk score. This risk score will be included as a covariate in efficacy analyses described in Section 7.

3.2.7 *Noncompliance with swabbing*

Noncompliance with daily nasal swabbing may result in missed endpoints and incompletely observed viral load trajectories.

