7. PRIMARY EFFICACY/EFFECTIVENESS ANALYSES

Time to event definitions

Except where specified, time is defined as calendar time as opposed to study time. The event occurs at the time of specimen collection for the first study swab positive for SARS-CoV-2.

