7.2 Primary efficacy analysis

Objective: To evaluate the effect of mRNA-1273 vaccination on acquisition of SARS-CoV-2 infection

Endpoint: Incident infection by study PCR subject to Outside Vaccination Censoring.

Data sets: Baseline SARS-CoV-2 negative participants enrolled as randomized

Exposure: Randomization, and number of study vaccine doses received within the Immediate Vaccination group

Adjustment covariates: Baseline factors: Age, sex, race/ethnicity, place of residence, attributes from the Baseline SARS-CoV-2 Infection Risk Assessment CRF

Analysis: Vaccine efficacy will be estimated using a time-varying Cox model that stipulates the following hazard function

$$h(t) = h_{0S}(t) \exp \{ \alpha_1 I(T_1 < t) + \alpha_2 I(T_2 < t) + \beta X \}$$

where t is time since study initiation (calendar time), T_1 is the calendar time of the first dose of study vaccine and T_2 is the calendar time of the second dose of study vaccine, $h_{0S}(t)$ is an unspecified baseline hazard that depends on study site, and X is a vector of baseline covariates identified in Section 3.2.5 and 3.2.6 as associated with exposure and/or censoring. The efficacy of one dose of study vaccine will be measured by $1 - e^{\alpha_1}$ and the efficacy of two doses measured by $1 - e^{\alpha_2}$. The model will be fit using the R survival package. Two-sided 95% confidence intervals for the VE estimates will be calculated using the Wald method.

If the set of covariates that is associated with SARS-CoV-2 exposure and/or censoring is too large to permit covariate adjustment, an IPCW analysis will be performed. Specifically, the above Cox model will be fit using a time-dependent weight that corresponds to a (standardized) probability of censoring. The analysis will be implemented using the R ipcswitch package.

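### The SAP omits, without giving a reason, the protocol's any-test VE analysis and any analysis of seroconversion, so no efficacy analysis checks whether swab-only detection differs between the open-label arms

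*SAP*

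**What the plan says.** **Primary endpoint.** Both documents take the primary event from study swabs. Protocol Section 6 says of real-time PCR on study swabs that "these data will be used to identify SARS-CoV-2 infection events for primary analysis". Protocol 6.4.3 dates the event at "the collection time of the first daily swab with a positive PCR test". SAP Section 7 agrees: "The event occurs at the time of specimen collection for the first study swab positive for SARS-CoV-2". SAP 7.2 repeats it: "Endpoint: Incident infection by study PCR subject to Outside Vaccination Censoring".

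**Secondary infection analyses in the protocol.** Section 6 states: "Secondary analyses of vaccine efficacy will include SARS-CoV-2 infection events diagnosed through any testing system". Section 6.4.3.2 gives the rule, "where the time of SARS-CoV-2 infection diagnosis is defined as the earliest of the first positive SARS-CoV-2 test result", with study PCR and external testing both counted. The same section applies the primary VE methods to seroconversion (secondary objective 2, antibody to nucleocapsid).

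**The SAP.** Section 2.2 still lists secondary objective 2. Section 3.2.3 defines the event: "A seroconversion event will be defined as the first instance of a positive serology result that follows at least one negative serology result". Section 3.2.4 says what a test means for that endpoint, and 3.2.8 sets the blood-sample exclusions used to derive it. After that, seroconversion is not analysed. Section 7.2.1 has an ITT-censored repeat and an all-FAS repeat, 7.2.2 mentions ITT censoring again, and Section 9 covers transmission (not performed), disease and variants.

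**Swabbing.** SAP 3.2.7 accepts that "Noncompliance with daily nasal swabbing may result in missed endpoints and incompletely observed viral load trajectories". It plans plots, tables and a GEE model of compliance, with covariates or IPCW if further predictors are found.

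**The concern.** Participants know their assignment and must swab themselves every day for an infection to be seen. Protocol 6.4.2 and 6.4.3.1 anticipated that adherence, and so ascertainment, might differ between groups, and promised at least sensitivity analyses. The any-test and seroconversion analyses are the planned infection analyses that draw on something other than the study swab. Without them, every efficacy result in the SAP depends on swab detection. That includes the disease endpoint in SAP 9.2, which needs a PCR-positive nasal swab.

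If one arm swabs less completely, fewer of its infections are found, and the Cox model attributes the shortfall to vaccine dose. The data for a check are scheduled in both randomised arms: a testing questionnaire about twice a week, and clinical serology at Months 0, 2 and 4 (Protocol Appendices E and F).

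**Working it through.** **1. Planned analyses against specified analyses**

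| Analysis | Protocol | SAP |
|---|---|---|
| Study-swab PCR infection | Primary (6, 6.4.3) | Primary (7.2) |
| Earliest of study PCR or external test | Secondary (6, 6.4.3.2) | None |
| Seroconversion | Secondary (6.4.3.2) | Objective, definition and censoring kept; no analysis |
| Secondary transmission | Secondary | Not performed; too few contacts (9.1) |
| Viral load | Primary 2 | Descriptive only; underpowered (7.3) |
| COVID-19 disease | Secondary | Modified; some symptoms not collected (9.2) |

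The SAP gives a specific reason for each of the last three changes. It gives none for rows two and three. Its general remark in Section 2, that some objectives cannot be addressed, does not identify them, and the change history names only 7.3.

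**2. The plan's own design figure**

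This point disputes no stated figure, but the design gives a scale. Inputs (Protocol Table 6-2 and 6.1): 6,000 per arm, 90% seronegative, 98% per-protocol, 4% incidence and 5% loss over 16 weeks, VE 50%, events counted from week 4.

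Weekly hazards: infection −ln(0.96)/16 = 0.00255; loss −ln(0.95)/16 = 0.00321. For infection hazard λ and loss hazard μ, P(event) = λ/(λ+μ) × [exp(−4(λ+μ)) − exp(−16(λ+μ))].

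- Unvaccinated: 6,000 × 0.90 × 0.98 × 0.0289 = 153.0
- Vaccinated (λ halved): 5,292 × 0.01464 = 77.5
- Total 230.5, against 225 stated (2.4% higher)

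Power at VE 57% against a null of 30%, one-sided 0.025: events 153.0 and 66.7, SE = √(1/153.0 + 1/66.7) = 0.147, |ln(0.43/0.70)| = 0.487, power = Φ(0.487/0.147 − 1.96) = 91.3%, against 90% stated. Both design figures are approximately reproduced.

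**3. Effect of unequal detection**

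Let m be the fraction of infections that study swabs miss in people who remain in the risk set. The documents give no value, so every m below is an assumption.

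Apparent VE = 1 − (1 − VE) × (1 − m_Imm)/(1 − m_SoC). With true VE 50%:

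| m Immediate | m Standard of Care | Apparent VE |
|---|---|---|
| equal | equal | 50.0% |
| 10% | 0% | 55.0% |
| 0% | 10% | 44.4% |
| 20% | 0% | 60.0% |
| 0% | 20% | 37.5% |
| 25% | 10% | 1 − 0.5 × 0.75/0.90 = 58.3% |
| 10% | 25% | 1 − 0.5 × 0.90/0.75 = 40.0% |

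**4. Effect of equal loss**

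This costs precision only. If both arms lose 20% of events, the SE of the log hazard ratio grows by 1/√0.8 = 1.118, about 12%. Design power at VE 57% (91.9% without the 98% factor) falls to 88.9%, 85.1% or 80.2% when 90%, 80% or 70% of infections are captured. SAP 2.5 calls the stopped trial underpowered, so none of these is its achieved power.

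**5. What SAP 3.2.4 and 3.2.7 do with a missed infection**

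- A participant stops swabbing and never resumes: censored at the last negative swab. Later time is not counted as infection-free, though the censoring may be informative.
- A participant is infected in a swab gap and later returns negative swabs: remains at risk and uninfected throughout. IPCW reweights for censoring, and this person was not censored. Covariates do not restore the event.

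The covariate vector in SAP 7.2 is also drawn from 3.2.5 and 3.2.6 and does not name 3.2.7.

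**The case against.** **The primary is unaffected.** A reader might infer that dropping these analyses is why infections found elsewhere go uncounted in the primary VE. The documents do not support that. The protocol's primary was always study-swab PCR, and the other two analyses were always secondary. What is lost is a check on the primary.

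**People who stop swabbing are not counted as infection-free.** They are censored at the last negative swab. The problem case needs every detectable day to be missed and swabbing then to resume, although Protocol 9.7 keeps daily swabbing going after diagnosis. This stands, and the frequency of such cases is unknown.

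**The SAP does look at compliance by arm.** SAP 3.2.7 leaves enrolment group out of the further predictors to adjust for, which could be read as ignoring differences between arms. That reading is too strong. The list also leaves out study time, calendar time and covariates already found in 3.2.5 and 3.2.6, terms the efficacy model largely carries, and the plots and tables are by enrolment group. Different swabbing would be visible. Even so, a group term cannot correct for different detection, because the difference is absorbed into the VE coefficients.

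**The alternative endpoints are imperfect.** Protocol 2.4 estimates that infrequent serology in the Phase 3 trials could miss 12–50% of asymptomatic infections, with bias of unknown direction. Outside tests depend on school programmes and on symptoms (Protocol 9.14 and 9.15), and symptom-driven testing may itself differ by arm. This stands, and it limits both analyses to sensitivity checks.

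**The SAP was cut back after early stopping**, and it treats the randomised analyses as post hoc. That makes a shorter list understandable, but it does not explain these two omissions, especially for an endpoint whose definition was kept.

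**Conclusion.** The point holds as an unexplained omission from the SAP. The any-test VE analysis is missing, and seroconversion is specified up to the point of analysis and no further. No efficacy analysis therefore tests whether swab-only detection differs between the open-label arms.

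The possible size depends entirely on assumed missed fractions. At true VE 50%, the cases shown range from 37.5% to 60.0%, and 25% against 10% gives 58% or 40% according to direction. The formula applies to missed infections in people who stay in the risk set, not to those who stop swabbing and lose person-time as well. With equal detection there is no bias, only lost precision. Nothing in the documents shows that detection did differ, and the primary endpoint itself follows the protocol.

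**What to change.** 1. **SAP 7.2.1:** add a supportive analysis with the event at the earliest positive study swab or reported outside test indicating acute infection. Use the Baseline SARS-CoV-2 negative participants enrolled as randomised, with the 7.2 model, the same covariates and outside-vaccination censoring. State how an outside positive that falls after the last negative study swab is counted.
2. **SAP Section 9:** add VE against seroconversion using the 3.2.3 and 3.2.4 definitions. Name nucleocapsid as the antigen, as in the protocol endpoint: 3.2.3 names none, and the vaccine encodes the S protein. The outside-vaccination rule in 3.2.4 is worded for RT-PCR and needs a serology equivalent.
3. If either analysis cannot be done, say so and give the reason, as SAP 9.1 does for transmission.

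Leave the primary model unchanged. Ending at-risk time at an outside positive would censor people at a known infection and depart from the protocol's primary.

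The cost is a few lines of SAP text and two model runs on data the protocol already schedules. The drawback is that outside tests are self-reported, of mixed type and partly symptom-driven, and that sparse serology misses some asymptomatic infections. Agreement with the primary would be reassuring; disagreement would need interpretation and would not replace the primary estimate.

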Baseline SARS-CoV-2 negative set (Main study primary data set): To account for ramping vaccine efficacy (VE), the protocol stipulated that primary analyses would be conducted among all baseline SARS-CoV-2 negative participants, and again among participants in the “Day 29 Negative Set”—the set of participants without seroconversion or PCR-confirmed infection on or prior to second vaccination on Day 29. The intent of this plan was to evaluate effects of the full two-dose vaccine regimen. Given that time of second vaccination is not easily defined in the SoC and Vaccine Declined groups and given that some participants in the Immediate Vaccination group began swabbing and accruing person-time and infection events before first vaccination, primary analyses will instead be conducted among all eligible enrolled baseline SARS-CoV-2 negative participants (Baseline SARS-CoV-2 negative set). All person-time and events will be included, and ramping VE will be accommodated using analyses that estimate vaccine effects according to number of doses received. Baseline SARS-CoV-2 negativity will be defined as PCR negative based on the first resulted (see section 3.2.9 for exclusions) nasal swab and seronegative based on the first qualifying (see section 3.2.8 for exclusions) blood sample closest to the first resulted swab. Note that blood collection for determining baseline serostatus was intended to occur coincident with initiation of swabbing; however, some participants had blood collected well before they began swabbing, and others had blood collected well after the initiation of swabbing. The analysis will summarize the distribution of time between first resulted swab and first blood. Qualifying blood sample closest to the first resulted swab date will be defined as either the closest qualifying blood sample on or before the first resulted swab date (if it exists) or the closest qualifying blood sample after the first resulted swab date (if no qualifying blood sample exists on or before the first resulted swab date). Primary analyses of vaccine efficacy against infection (VES) and of the vaccine effect on viral load (ΔVL) will be conducted among Baseline SARS-CoV-2 negative set participants that were enrolled as randomized.

All primary and secondary analyses will be done according to enrollment group, ie, Immediate Vaccination Group, Standard of Care Group, or Vaccine Declined Group.

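### The primary Cox model codes the two doses cumulatively but reads two-dose efficacy from the second coefficient alone, which compares two doses with one dose rather than with none

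*SAP*

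**What the plan says.** SAP 7.2 is the primary efficacy analysis for primary objective 1. It specifies a Cox model on calendar time, with a site-specific baseline hazard. The dose terms and covariates in the exponent end in "I(T_1 < t) + \alpha_2 I(T_2 < t) + \beta X", with α1 multiplying the first indicator.

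The two times are defined plainly: "T_1 is the calendar time of the first dose of study vaccine" and "T_2 is the calendar time of the second dose of study vaccine". No condition ends the first indicator when the second begins.

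The effect measures follow. "The efficacy of one dose of study vaccine will be measured by" 1 − exp(α1), "and the efficacy of two doses measured by" 1 − exp(α2). The section adds that two-sided 95% "confidence intervals for the VE estimates will be calculated using the Wald method".

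SAP 3.1 explains what the model is for. The protocol's Day 29 Negative analysis was meant to isolate the complete two-dose course. The SAP drops it as a primary analysis, keeps all person-time and events, and says that "ramping VE will be accommodated using analyses that estimate vaccine effects according to number of doses received".

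**The concern.** The two indicators are nested. A participant who has had dose 2 has also had dose 1, so both indicators equal 1 from then on. In such a model the second coefficient is an increment: what dose 2 adds to dose 1. Calling 1 − exp(α2) the efficacy of two doses gives that increment the name of a different quantity.

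The plan has given up the Day 29 restriction and relies on this model to separate the effect of the full course from the ramp-up period. If the formula is followed literally, the two efficacies reported together have different reference groups: no vaccine for one dose, and one dose for two doses. A reader would take both as efficacy against no vaccine. An effective two-dose regimen could then appear weak, or no better than nothing, because much of its benefit had already been credited to dose 1.

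**Working it through.** **The plan's own figure.** No number in either document depends on 1 − exp(α2), so there is none to reproduce for the formula itself. The closest reference value is the design statement (Protocol 6.1, SAP 2.5) of 90% power for efficacy above 57%, with the null of at most 30% given in Protocol 6.1. Protocol Table 6-7 gives about 150 unvaccinated post-Day 29 events. With 0.43 × 150 = 64.5 vaccinated events:

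- SE of the log hazard ratio = √(1/150 + 1/64.5) = 0.149
- ln(0.70/0.43) = 0.487
- power = Φ(0.487/0.149 − 1.96) = 90.5%

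This agrees with the stated 90%. The 57% is used below as a true two-dose efficacy on the plan's own scale.

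**Algebra.** Take the hazard as written, at fixed site, calendar time and covariates:

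| State | First indicator | Second indicator | Hazard ratio vs unvaccinated |
|---|---|---|---|
| Unvaccinated | 0 | 0 | 1 |
| After dose 1, before dose 2 | 1 | 0 | exp(α1) |
| After dose 2 | 1 | 1 | exp(α1 + α2) |

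Hence exp(α2) = exp(α1 + α2)/exp(α1), the hazard ratio for two doses against one. Write VE1 and VE2 for the true efficacies of one and two doses against no vaccine. The SAP formula then returns

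1 − exp(α2) = 1 − (1 − VE2)/(1 − VE1).

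For example, with VE1 = 30% and VE2 = 57%: 1 − 0.43/0.70 = 38.6%.

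**Size.** VE1 is not in the documents (Protocol Table 6-2 says the calculations do not use efficacy before 14 days after the first vaccination), so it is varied as an assumption. Entries are the two-dose efficacy that the SAP formula would report:

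| Assumed VE1 | True VE2 = 57% | True VE2 = 70% | True VE2 = 90% |
|---|---|---|---|
| 0% | 57.0% | 70.0% | 90.0% |
| 20% | 46.2% | 62.5% | 87.5% |
| 30% | 38.6% | 57.1% | 85.7% |
| 40% | 28.3% | 50.0% | 83.3% |
| 50% | 14.0% | 40.0% | 80.0% |
| 60% | −7.5% | 25.0% | 75.0% |
| 70% | −43.3% | 0.0% | 66.7% |

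The corrected contrast, 1 − exp(α1 + α2), returns the column heading in every row. When the two true efficacies are equal, the SAP formula returns zero.

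**Check by fitting.** Cox data were simulated for 60,000 participants, with true VE1 = 30%, true VE2 = 57%, doses 28 days apart, and incidence raised fivefold for precision.

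| Coding | 1 − exp(a1) | 1 − exp(a2) | 1 − exp(a1 + a2) |
|---|---|---|---|
| Nested, as in SAP 7.2 | 32.7% | 35.9% | 56.8% |
| Mutually exclusive dose states | 32.7% | 56.8% | not a meaningful contrast |

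Under the nested coding, 1 − exp(a2) sits near its theoretical 38.6% and well away from 57%. The sum recovers two-dose efficacy and equals the estimate from exclusive coding.

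**Interval.** In the same fit the standard error was 0.0465 for a2 and 0.0278 for a1 + a2. The Wald interval for a2 is therefore centred on the wrong value. Here it is also about 0.0465/0.0278 ≈ 1.7 times as wide on the log scale, because the increment depends on the few infections in the short window between doses.

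**The case against.** The strongest reply is that the slip may lie only in the printed equation. SAP 7.1 divides follow-up into unvaccinated, one-dose and two-dose periods that do not overlap, and 7.2 names the number of study doses as the exposure. An analyst who enters those periods as a factor obtains two-dose efficacy correctly as 1 − exp(α2). The documents contain no code and no results, so it cannot be said that a wrong figure was produced. This stands as a limit on the claim. It also shows that the intended comparison is two doses against none, which the written model and formula do not give. Neither document ends the first indicator at dose 2 or describes α2 as an increment.

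It can also be said that the size is hypothetical. That is fair: with VE1 = 30% and VE2 = 90% the error is only 4.3 points, while elsewhere in the table the estimate turns negative. The direction is not in doubt if one dose protects.

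Third, SAP 2.4 treats the randomized analyses as post hoc and SAP 2.5 calls the study underpowered. That lowers the stakes, but 7.2 is still labelled the primary efficacy analysis and still specifies estimates and intervals.

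Finally, the reach into other sections varies. The ITT analysis in 7.2.1 repeats the primary analysis explicitly. Section 7.2.2 points to a model in 7.1.1, a section that does not appear. Section 9.2 asks only for estimation analogous to the infection endpoint. Inheritance of the formula is therefore clear for the first and a natural reading for the other two.

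**Conclusion.** As written, the two-dose efficacy in SAP 7.2 is defined wrongly for the model it comes from. It measures dose 2 over dose 1, and so does its Wald interval. This follows from the equation alone and needs no assumption. The definition is correct only if α1 = 0.

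The size depends on one-dose efficacy, which the documents do not give. For a true two-dose efficacy of 57%, the reported value falls from 57.0% to −7.5% as assumed one-dose efficacy rises from 0% to 60%. For a true 90%, it falls from 90.0% to 66.7% as one-dose efficacy rises from 0% to 70%.

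The model itself is sound. One-dose efficacy, the descriptive incidence rates in 7.1, and the design power and event counts are unaffected. Because the definition serves primary objective 1, it should be corrected before any two-dose efficacy is reported.

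**What to change.** Either of two changes is exact:

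1. Make the dose states mutually exclusive: α1·I(T1 < t ≤ T2) + α2·I(T2 < t), with the first indicator staying on if dose 2 is never given. Then 1 − exp(α1) and 1 − exp(α2) both compare with no vaccine, and the Wald intervals apply as written. This matches the exposure periods in SAP 7.1 and is the simpler choice.
2. Keep the nested indicators and report two-dose efficacy as 1 − exp(α1 + α2). Take the Wald interval from Var(a1) + Var(a2) + 2Cov(a1, a2) on the log scale, then transform. If the increment 1 − exp(α2) is also of interest, label it as dose 2 against dose 1.

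Use the same definition in the weighted version of the model in 7.2, the supportive and exploratory analyses in 7.2.1 and 7.2.2, and the COVID-19 disease analysis in 9.2. Correct the reference to 7.1.1 in 7.2.2 at the same time.

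The cost is one line of SAP text and one line of code. No data, design or sample size changes. If the nested model has already been fitted, the correct estimate and interval can be recovered from its coefficients and covariance matrix.
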